### Comparators

Pharmacological treatment options for patients with schizophrenia who are nonresponsive to antipsychotic monotherapy will include (1) initiation of a second antipsychotic, (2) initiation of an antidepressant, (3) initiation of a mood stabilizer and (4) initiation of a benzodiazepine.

Within each clinical subgroup, treatment options may be refined by exclusions at the drug class or individual agent level. For example, antidepressants are generally not considered treatment alternatives in patients presenting with mania, but could reasonably be considered for patients in the remaining four schizophrenia subgroups: depression, anxiety, schizoaffective disorder, and uncomplicated schizophrenia. Unless it is not considered a reasonable treatment option for a specific subgroup, initiation of a new antipsychotic will serve as the reference category because it is a frequently recommended approach to improving treatment response and is a common treatment strategy across all of the clinical subgroups under study. A survey on the prescribing behaviors of clinicians who prescribe psychotropic medications for individuals with schizophrenia will inform these choices.

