### *Propensity score estimation and application*

Propensity score methods involve two steps: estimation of the propensity scores and application of the propensity score. Estimation of the propensity scores involves decisions about which covariates to include in the prediction model of the propensity scores and what form the model should take. We will use expert opinion to select the variables to include in the propensity score. To estimate the propensity scores we will first use logistic regression including all baseline predictors occurring prior to treatment assignment. In addition, we will augment our analysis with another non-parametric method for building the propensity score model such as a generalized boosting algorithm implemented with regression trees. We will assess the sensitivity of our results to the choice of the propensity score model.

For the application of the propensity scores, we will use weighting by the odds to estimate the average treatment effect on the treated sample and weighting by the inverse probability of treatment weights to estimate the average treatment effect in the population.

We will examine the covariate balance using standardized differences in covariate means across the treatment groups after weighting, and address any significant imbalances.

**AIM 2 Heterogeneity of Treatment Effects:** Within the five subgroups, explore whether the comparative effectiveness and safety of alternative treatment strategies varies according to patient age and presence of a substance use disorder.

We will use similar Cox model techniques for the HTE analyses. First we will assess interaction of age and substance use variables with treatment. If such interactions are found, we will then perform analyses examining alternative treatment strategies stratified by age group or substance use.

The rationale for investigating patient age as a moderator of antipsychotic treatment effects follows from evidence that individuals early in the course of psychosis may respond differently to medications than people with more chronic illness. The rationale for investigating comorbid diagnosis of a substance use disorder as a moderator of treatment effects follows from evidence that people diagnosed with schizophrenia and comorbid substance use disorders respond more poorly to antipsychotic medications than those without comorbid substance use disorders.

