### Sample size

Table 5 presents sample size estimates for national 2001-2010 Medicaid data based on our preliminary analyses. For example, we expect that the following treatments with corresponding numbers will be options for the depression symptom subgroup: second antipsychotic (n = 2,192), mood stabilizer (n = 1,296), antidepressant (n = 4,646), and benzodiazepine (n = 1,199). We will then, for example, compare 2,192 patient episodes with a second antipsychotic to 2,192 propensity-score matched patient episodes that were treated with an antidepressant. The 1:1 matching method uses a nearest neighbor algorithm. As recommended for observational studies, we will use a caliper width of 0.2 of the standard deviation of the logit of the propensity score to ensure appropriate matching.

Our power analysis is based on two-sided ( $\alpha = .05$ ) tests for differences in proportions between treatment groups, which depend upon the sample size of each group and the probability of the outcome. To demonstrate power, we conservatively use the expected number of distinct patients rather than episodes (distinct patients equal approximately 70% of the episodes in Table 5). Final statistical analyses of individual episodes will have greater power (i.e., be able to detect even smaller percent differences) and will incorporate random effects to account for patients who contribute more than one episode.

Table 5: Estimated sample sizes of selected schizophrenia treatment episodes (2001-2010)

	Uncomplicated Schizophrenia	Schizoaffective Disorder	Depression	Mania	Anxiety
Second Antipsychotic	27,005	6,393	2,192	1,580	611
Mood Stabilizer	9,954	4,734	1,296	2,107	NA
Antidepressant	25,061	9,692	4,646	NA	1,110
Benzodiazepine	12,248	3,681	1,199	840	1,099

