We demonstrate the smallest detectable differences in proportions with >80% power for three examples. For example, in the depression group, 1534 distinct patients per group (70% of 2,192) distinct patients per group (antidepressant vs. second antipsychotic) will provide at least 80% power to detect a difference of 5.0% in the rate of hospital admission in 1 year of follow-up. Also within the depression group, the smallest treatment group (839 distinct patients of 1,199 initiating episodes of benzodiazepines), will provide at least 80% power to detect differences of 6.8% between the reference and the comparator group. In the smallest group overall (611 episodes in anxiety patients starting mood stabilizers), there is still >80% power to detect differences as small as 10.0% in their outcomes compared to those with anxiety in the comparator group. Because of the larger sample sizes, all comparisons in the uncomplicated schizophrenia and schizoaffective disorder groups will have power much greater than 80% to detect a 4% difference in proportions.

These large sample sizes permit identification of statistically significant differences of small magnitude, not all of which may have substantial clinical and policy importance. We will work with our patient, clinical, and policy stakeholders to interpret the meaning of the magnitude of observed treatment effects. The ability to detect small differences (Aim 1) will enable detection of clinically meaningful treatment heterogeneity (Aim 2).

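### Aim 2 estimates age and substance-use strata only after an interaction is found, with no threshold, test form or error control, so the stratum differences it produces are selected and exaggerated

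*Combined protocol and SAP*

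**What the plan says.** The Analysis plan words Aim 2 as exploration, with age and substance use disorder as the two moderators: "Within the five subgroups, explore whether the comparative effectiveness and safety of alternative treatment strategies varies according to patient age and presence of a substance" […]. It sets out two steps within Cox models. The first is "First we will assess interaction of age and substance use variables with treatment". The second is conditional on the first: "If such interactions are found, we will then perform analyses examining alternative treatment strategies stratified by age group or substance use".

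The plan does not say what counts as finding an interaction, whether the terms are tested jointly or one at a time, how age is grouped for this purpose, or which outcomes are covered. The only age bands are the twelve listed for the propensity score in Appendix 2. No multiplicity adjustment appears anywhere. The one significance level, two-sided 0.05, belongs to the power analysis under Sample size, which concerns "tests for differences in proportions between treatment groups". That section ends by stating that the ability to detect small differences in Aim 1 "will enable detection of clinically meaningful treatment heterogeneity (Aim 2").

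Under Comparators, "initiation of a new antipsychotic will serve as the reference category", unless it is not a reasonable option for a subgroup.

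**The concern.** A gate of this kind raises two problems.

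- **False triggers.** Several treatment contrasts, two moderators and five clinical subgroups give many chances for one interaction to reach significance by luck. The plan leaves the size of that risk open, because it fixes neither the threshold nor the form of test.
- **Selection.** Stratified effects are estimated only where the interaction estimate was large enough to pass. The differences between strata that emerge are therefore too large on average. Cells that did not pass yield no stratum estimates for comparison.

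The study aims to inform personalised treatment choices, and the Sample size section speaks of detecting clinically meaningful heterogeneity. Age-specific or substance-use-specific effects that come through this gate could be given more weight than they can bear.

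**Working it through.** **The plan's own figures.** There is no error rate or power for Aim 2 to reproduce. The nearest figures are the Aim 1 power statements. For n per group and proportions p1 and p2 with mean p̄, power = Φ{[|p1−p2|√n − 1.96√(2p̄(1−p̄))] / √[p1(1−p1)+p2(1−p2)]}. No base rate is given, so I centre the rates on 50%, the worst case:

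- 1,534 per group, difference 5.0%: Φ[(1.958−1.386)/0.706] = 79.1%
- 839 per group, difference 6.8%: 79.6%
- 428 per group (70% of 611), difference 10.0%: 83.4%

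These agree with the stated 80% to within a percentage point or exceed it. They concern main effects only.

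**Number of interaction terms, psychiatric hospitalization.** Contrasts per subgroup equal the treatment options minus one.

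- Uncomplicated, schizoaffective and depressive: four options, three contrasts each.
- Mania: two contrasts, since "antidepressants are generally not considered treatment alternatives in patients presenting with mania".
- Anxiety: two contrasts, since the Table 5 row reads "Mood Stabilizer 9,954 4,734 1,296 2,107 NA", with the last entry for anxiety.

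The total is 3+3+3+2+2 = 13. With two moderators, each taken as one degree of freedom, there are 13 × 2 = 26 terms in 5 × 2 = 10 subgroup-by-moderator cells.

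**False triggers with no true heterogeneity, alpha 0.05 assumed.**

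- One joint test per cell: 1 − 0.95^10 = 40.1%.
- 26 separate tests, if independent: 1 − 0.95^26 = 73.6%.
- 26 separate tests, allowing for the shared reference arm: 70.1% by simulation with Table 5 sizes, 69.4% with equal arms.
- Within one cell: 5% with a joint test. With separate terms, 1 − 0.95^2 = 9.8% for two and 1 − 0.95^3 = 14.3% for three if independent, and slightly less with the shared reference.

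**Sensitivity to the unstated choices.**

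| Alpha per test | 10 joint tests | 26 separate terms (shared reference to independent) |
|---|---|---|
| 0.01 | 9.6% | 22–23% |
| 0.05 | 40.1% | 70–74% |
| 0.10 | 65.1% | 91–94% |

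**Exaggeration from the gate.** Let the true interaction be δ standard errors. Its mean estimate, given that it is significant in the right direction, is δ + φ(1.96−δ)/Φ(δ−1.96). For 30% power δ = 1.435, so the mean is 1.435 + 0.348/0.300 = 2.59, which is 2.59/1.435 = 1.8 times the truth. At 80% power δ = 2.80, the mean is 3.15 and the ratio is 1.13. The plan gives no interaction power, so 30% is an illustration.

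**The case against.** The strongest reply is that Aim 2 is worded as exploration, has only two moderators, and gives a rationale for each. Exploratory work need not control a family-wise error rate. The Sample size section itself warns that significant differences may lack clinical or policy importance, and commits to interpreting their magnitude with stakeholders. This stands. It is why adjustment across the tests should be optional. It does not supply a criterion or remove the selection.

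Several stronger readings are tempting, and the documents do not support them.

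- **That false stratified results would appear 70% of the time.** This needs alpha 0.05 for interactions, separate tests of each term, and any one term acting as trigger. None of these is stated, and the text fits a joint test equally well.
- **That the rule hardly discriminates.** Within one cell the false-trigger rate is 5% to about 14%. The larger figures come from pooling five clinical populations and two moderators.
- **That 26 is a minimum.** The Comparators section lets options be refined by subgroup, which could lower the count. It could also rise to 14 × 2 = 28, because the power text describes the 611 anxiety episodes as mood-stabilizer starts, whereas Table 5 lists them under second antipsychotic.
- **That null interactions will be withheld.** The plan conditions the stratified analyses on a finding. It does not say that interaction tests without one go unreported.

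The clinical subgroups may also overlap, since only the uncomplicated group is defined by the absence of the others. Overlap would correlate the tests and tend to lower the pooled figures, by an amount the documents do not allow one to compute.

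Finally, ungated reporting means stratum estimates always appear, even under the null. That is true, but the harm is selective estimation. A complete set shown beside its interaction tests does not carry that bias.

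**Conclusion.** The concern holds in a conditional form. Aim 2 uses an undefined significance gate to decide which stratum effects are estimated, and has no error control. At two-sided 0.05 with no heterogeneity, the chance of at least one false trigger on the primary outcome is about 40% with ten joint tests and about 70% with 26 separate terms. Both figures assume the Table 5 comparators, one degree of freedom per moderator, and no overlap between clinical subgroups. The firmer point is the selection, which inflates stratum differences whatever threshold is used. The inflation is large where interaction power is low (about 1.8-fold at 30% power) and small where power is high. This should be changed, but it does not affect the Aim 1 analyses.

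**What to change.** In the Aim 2 text of the Analysis plan:

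1. For psychiatric hospitalization, specify one joint test of the treatment-by-moderator terms per clinical subgroup and moderator, ten tests in all.
2. Remove the condition on estimation. Give stratum-specific effects with confidence intervals, and the interaction p-value, for every subgroup and moderator whatever the test shows. This requires the age groups to be named in advance.
3. State how many interactions were tested, and label Aim 2 results as exploratory, including those on other outcomes.
4. Treat Holm adjustment across the ten tests as optional. It is needed only if a confirmatory claim of heterogeneity is to be made, and it costs power.

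No new data are required. The cost is SAP wording and a larger supplementary table: with two strata per moderator, 26 × 2 = 52 stratum estimates on the primary outcome. Many will be imprecise and should be read together with the interaction tests.

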## **AIM 3 Instrumental Variable and Other Sensitivity Analyses**

### *Instrumental variable analyses*

We will also seek to use instrumental variable analyses to control for unobservable confounders. First, we will try to identify a feasible instrument and, if one is identified, we will apply it to our analyses. Instruments to be considered includes zip code, county, or state of patient residence; and, if there are significant time trends in the use of medications, year of prescription. We will also consider the prescribing patterns of prescribers but are concerned that this data may not be reliably available in the data.

If the candidate instrument meets the following basic criteria, we will integrate it into our statistical analyses: 1) the instrument is associated with use of the treatment; 2) the instrument does not cause the outcomes except through its relationship with the treatment (known as exclusion restriction); and 3) the instrument is not confounded with the outcomes (known as independence assumption).

We will evaluate the plausibility of exclusion restriction by examining whether a candidate instrumental variable is related to potentially hazardous co-prescriptions, and study whether the independence assumption needs to be made conditionally on observed patient characteristics. We will employ methods rigorously developed for causal inference using instrumental variables, such as instrumental variable propensity score methods or near-far matching. These methods are applicable to various types of outcomes and to situations where the instrument is related to observed patient characteristics. These methods involve construction of instrument groups that, by weighting or matching, are similar in terms of observed covariates but differ in the instrument values. With these methods, treatment effects can be estimated by difference-in-difference, i.e., the ratio of the average outcome difference over the average treatment difference between the instrument groups. A complication of instrumental variable analysis is that the causal estimands inferred are in general distinct from the average treatment effects, overall or on the treated samples, as in the intention-to-treat analysis. We will perform bounding and sensitivity analyses to investigate the relationship between the instrumental variable estimates and intention-to-treat estimates and examine its implications for the interpretation of the final results.

### Sensitivity Analyses

We will conduct sensitivity analyses to confirm findings from the primary analyses and to examine their generalizability. In addition to the primary 360-day intention-to-treat analyses we will conduct 180-day intention-to-treat analyses and as-treated analyses. Another sensitivity analysis will examine subgroups of people with depression, anxiety, or mania diagnoses that are listed by more than one provider.

**Quantitative Sensitivity Analyses for Unmeasured Confounders.** Because the observed relative risk is a closed-form function of the balance of confounders among exposure groups, the strength of the confounder, and the prevalence of the confounder, it is possible to estimate the extent of unmeasured and thus unadjusted confounding necessary to fully explain the observed findings, i.e., would move the observed relative risk to statistical insignificance (the null).

To quantify how strong unmeasured confounding would have to be to explain the observed effect sizes among our comparison groups, we will use the array approach to understand how the strength of unmeasured confounders with known associations with our outcomes, such as BMI and risk of diabetes, and the confounder imbalance among study groups might affect the observed relative risk.

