## Protocol Details

### Overview of study design

The study is a retrospective cohort study of adults with schizophrenia that will compare outcomes of new users of alternative psychotropic medication strategies using 10 years of Medicaid data. The primary comparative effectiveness analyses will focus on subgroups of patients with schizophrenia facing common clinical situations.

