### Subgroups

From the base study population described above, 5 clinical subgroups will be defined based on the presence of psychiatric diagnoses during the 30 days prior to and inclusive of the treatment change under study (index date) and who have this same diagnostic code from more than one provider to increase the validity of the diagnostic groups. The subgroups will be defined by codes to capture 1) uncomplicated schizophrenia (with schizophrenia codes from at least 2 different providers and without any diagnoses that would qualify them for the other subgroups during the 365 days prior to the index date), 2) schizoaffective disorder (ICD-9: 295.7) as the most recent schizophrenia-spectrum diagnosis, 3) depressive (ICD-9: 293.83, 296.2, 296.3, 296.9, 298.0, 300.4, 311), 4) manic (296.0, 296.4-296.8), and 5) anxiety (293.84, 300.00-300.02, 300.09, 300.20-300.23, 300.29, 300.3, 300.7, 308.0-308.9, 309.21, 309.81, 312.39, 313.0, 313.21, 313.23). These subgroups are defined to reflect the reason for the change in treatment.

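### The multi-provider sensitivity analysis for depression, anxiety and mania is essentially redundant, because the primary subgroup definition already requires more than one provider

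*Combined protocol and SAP*

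**What the plan says.** The Subgroups section opens with a general sentence covering every subgroup: "5 clinical subgroups will be defined based on the presence of psychiatric diagnoses". The diagnoses are to fall in the 30 days ending on the index date, and the same sentence limits membership to patients "who have this same diagnostic code from more than one provider to increase the validity of the diagnostic groups". The entry for uncomplicated schizophrenia repeats the idea in its own terms: "with schizophrenia codes from at least 2 different providers".

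The Overview of study design makes these subgroups the setting of the main comparisons: "The primary comparative effectiveness analyses will focus on subgroups of patients with schizophrenia facing common clinical situations".

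The Sensitivity Analyses section, under Aim 3, states its purpose: "We will conduct sensitivity analyses to confirm findings from the primary analyses and to examine their generalizability". After the 180-day and as-treated analyses it adds one in "subgroups of people with depression, anxiety, or mania diagnoses that are listed by more than one provider". It gives no other time window, number of providers, provider type or claim setting.

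Table 5, under Sample size, gives expected episode counts by subgroup and treatment. It does not say which provider rule was used to count them.

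**The concern.** A sensitivity analysis is informative when it changes an assumption that the primary analysis makes. Here the assumption is how sure one must be of the depression, anxiety or mania diagnosis before placing a patient in that subgroup. The primary definition and the sensitivity definition both set the bar at more than one provider, so the assumption does not change.

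This matters because the plan leans on these diagnoses. Approach to confounding and Limitations both present the restriction to diagnostic subgroups as a main protection against confounding by indication. Whether the results hold when the diagnosis is less certain is therefore a question of substance.

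There is a second consequence. Read alone, the sensitivity sentence suggests that the primary subgroups need only one provider. Two analysts working from this plan could build different primary cohorts, and Table 5 would not tell them which was meant.

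**Working it through.** No formula in the plan bears on this, so the check sets the two definitions side by side.

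| Element | Primary rule (Subgroups) | Sensitivity rule (Sensitivity Analyses) |
|---|---|---|
| Subgroups covered | All five, by the general sentence | Depression, anxiety, mania |
| Providers required | More than one | More than one |
| What must agree | The same code | The diagnosis; code agreement not mentioned |
| Window | 30 days up to the index date; not stated whether the second provider's code must fall inside it | None stated |

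Call the patients who meet the primary rule P and those who meet the sensitivity rule S.

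1. *Is everyone in P also in S?* Yes, on the wording given. A patient with one code from two providers has that diagnosis recorded by two providers, and S adds no further condition.
2. *S as a filter on the primary subgroups.* The patients kept are those in both P and S, which is P. Nobody is removed.
3. *S as a fresh definition on the base cohort.* S can exceed P in two ways. Two providers may have used different codes in one category: for example, 296.3 from one and 311 from another, both in the plan's depressive list. Or the second provider's code may lie at another time, if the primary rule is read as needing both codes in the 30 days. These patients would be added.
4. *Does either use bring in patients diagnosed by a single provider?* No. Both rules exclude them, so the contrast between one-provider and multi-provider diagnoses is never made.
5. *When would the check be informative as worded?* If P required only one provider, S would be a true restriction. The Subgroups section says otherwise.

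**Extent, from Table 5.** Contrasts with a second antipsychotic number 3 (uncomplicated), 3 (schizoaffective), 3 (depression), 2 (mania) and 2 (anxiety), in total 13. The three subgroups named in the sensitivity analysis hold 3 + 2 + 2 = 7.

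Episodes in those three subgroups:

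- Depression: 2,192 + 1,296 + 4,646 + 1,199 = 9,333
- Mania: 1,580 + 2,107 + 840 = 4,527
- Anxiety: 611 + 1,110 + 1,099 = 2,820

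Together these make 16,680. The other two subgroups hold 74,268 and 24,500, so the table sums to 115,448 and the share is 16,680 / 115,448 = 14.4%. The plan does not say that the subgroups are mutually exclusive, so this sum may count some episodes more than once.

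**The case against.** The strongest reply is that the two rules are not worded alike. The primary rule asks for the same code and sits in a sentence with a 30-day window. The sensitivity rule asks only for the diagnosis and names no window. The section's aims include generalizability, which fits a somewhat broader group. On that reading the analysis could include extra patients and give different estimates.

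This stands, and it limits the point. A reader might infer that the sensitivity analysis must select exactly the same patients and return the same hazard ratios. The documents do not support that, because step 3 leaves room for additions. If sameness of code means sameness of category, the overlap is close to complete; if it means the literal code, the overlap is smaller by an amount that the plan does not let one calculate. What the reply does not supply is a test of diagnostic certainty, since patients with a single provider stay out on every reading.

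A reader might also infer a loss of power. That would need Table 5 to have been counted under a one-provider rule, and a retention proportion under the stricter rule. The documents give neither. If Table 5 already used the multi-provider rule, the loss is nil.

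Nor do the documents show that a repeated result would be presented as independent confirmation. If the cohorts coincided, identical counts would reveal it.

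Finally, the scope is limited. The two largest subgroups are not named in this check. The 180-day, as-treated, alternative propensity-model, instrumental-variable and unmeasured-confounding analyses do not depend on it. The primary provider rule can be followed as written.

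**Conclusion.** The point holds as one of redundancy and inconsistency between two current passages. The sensitivity analysis adds essentially no information on the question it appears to address, and its wording implies a primary rule that the Subgroups section contradicts. It should be corrected, although it does not invalidate the primary analysis.

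The conclusion rests on two readings: that the provider clause in the opening sentence of Subgroups governs all five subgroups, as its position indicates, and that the sensitivity analysis carries no unstated window or provider condition. A stated window that differed from the primary one could make the analysis distinct, but none is given. The count of 7 in 13 contrasts takes a second antipsychotic as the reference throughout, which the Comparators section allows to vary by subgroup. No effect on power or on the estimates is claimed.

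**What to change.** Reconcile the two sections in one of two ways. The documents do not settle which was intended.

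- **Multi-provider rule as primary.** Leave the Subgroups section as it is and redefine the sensitivity analysis as depression, anxiety and mania subgroups with a qualifying code from at least one provider in the 30-day window.
- **One-provider rule as primary.** Remove the multi-provider condition from the general sentence in Subgroups and keep the sensitivity analysis as the stricter check.

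Under either choice, state whether the second provider's code must match exactly or only by category, whether it must fall in the 30 days, and which rule produced the Table 5 counts. Because uncomplicated schizophrenia is defined partly by the absence of diagnoses qualifying for other subgroups, also say whether a single-provider code is enough to exclude a patient from it.

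The cost is a sentence or two in the plan and one cohort re-run on data already held.

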## Outcomes of interest

### Primary

The primary effectiveness outcome will be time to psychiatric hospitalization.

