## Approach to confounding

Physicians make treatment choices in light of available clinical information and as a result there is a risk of confounding by clinical indication for the treatments under study. Our design minimizes confounding by indication by focusing on diagnostic subgroups. To further reduce confounding, we will control for a broad range of potentially relevant factors from claims histories. These factors will be identified in the 365-day period before drug initiation and used to calculate propensity scores. In addition we will conduct sensitivity analyses to estimate the extent of unmeasured confounding necessary to fully explain our observed findings and we will conduct instrumental variable analyses if a suitable instrument is identified.

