## Analysis plan

**AIM 1 Comparative Effectiveness: Main Effects:** Within five clinically important schizophrenia subgroups, compare the effectiveness and safety of alternative medication strategies beyond antipsychotic monotherapy.

We will construct Cox models to estimate effects of the study treatments. We will first examine unadjusted treatment effects and then will conduct analyses using basic adjustment for demographic factors. Then we will construct Cox models using weighted propensity scores. Follow-up time will be censored at discontinuation or change of second drugs, death, or loss of Medicaid.

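### The unmeasured-confounding analysis defines full explanation of a finding as loss of statistical significance, which is a weaker threshold that depends on sample size

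*Combined protocol and SAP*

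**What the plan says.** Two sections commit to this analysis. Approach to confounding says that sensitivity analyses will "estimate the extent of unmeasured confounding necessary to fully explain our observed findings". The paragraph on quantitative sensitivity analyses, in the Sensitivity Analyses section under Aim 3, says that "it is possible to estimate the extent of unmeasured and thus unadjusted confounding necessary to fully explain the observed findings", and explains this as confounding that "would move the observed relative risk to statistical insignificance (the null".

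The next paragraph of that section states the aim differently: "To quantify how strong unmeasured confounding would have to be to explain the observed effect sizes among our comparison groups". The method there is an array: "we will use the array approach to understand how the strength of unmeasured confounders with known associations with our outcomes". BMI and diabetes is given as an example.

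The reasoning is on the relative-risk scale: "the observed relative risk is a closed-form function of the balance of confounders among exposure groups". The treatment effects come from elsewhere: "We will construct Cox models to estimate effects of the study treatments", under Aim 1. The plan does not print the bias formula, say how a hazard ratio becomes the observed relative risk, or give confounder prevalences, event risks or a tipping value.

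**The concern.** Confounding that fully explains a result carries the estimate to 1. Confounding that removes significance carries only the nearer confidence limit to 1, and can leave most of the estimated effect in place. The plan's explanatory clause treats the two as the same and gives the weaker one the name of the stronger. Two programmers could follow the text faithfully and produce different numbers under one label.

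The clause is the most specific definition that the plan offers. The analysis also carries weight: the instrumental-variable analysis goes ahead only if a suitable instrument is found, so this may be the only analysis aimed directly at unmeasured confounding that is actually run. Under the significance definition, the same effect with the same confounding structure would look fragile in a small subgroup and sturdy in a large one, purely because of the width of the interval.

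**Working it through.** **No plan figure to reproduce.** The documents give no tipping point, so what follows is an illustration.

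**Inputs from the plan.** Distinct patients are about 70% of the episodes in Table 5. The smallest cell has 611 episodes, giving 428 patients. The depression comparisons use 839 and 1,534 per group. In uncomplicated schizophrenia, second antipsychotic is 0.70 × 27,005 = 18,904 and antidepressant is 0.70 × 25,061 = 17,543.

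**Assumptions, not in the documents.** Hazard ratio 1.3; one-year risk 25% in the reference arm; constant hazards; one binary confounder with prevalence P1 = 50% in one arm and P0 = 20% in the other; and the standard formula

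RR_obs = RR_true × [P1(R − 1) + 1] / [P0(R − 1) + 1],

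where R is the confounder's strength. With RR_true = 1 and RR_obs = t this gives R = 1 + (t − 1)/(P1 − P0·t).

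**Threshold A, estimate reaches 1** (t = 1.3): R = 1 + 0.30/(0.50 − 0.26) = 2.25. Sample size does not enter.

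**Threshold B, lower limit reaches 1.** Risk in the other arm is 1 − 0.75^1.3 = 0.312. Events = n × (0.25 + 0.312) for equal groups. SE of the log hazard ratio = 1/√[events × a(1 − a)], with a the share of patients in one arm. Lower limit = 1.3 × exp(−1.96 × SE).

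| Patients per group | Events | SE | Lower limit | R, limit to 1 | R, estimate to 1 |
|---|---|---|---|---|---|
| 428 | 240 | 0.129 | 1.010 | 1.03 | 2.25 |
| 839 | 471 | 0.092 | 1.085 | 1.30 | 2.25 |
| 1,534 | 862 | 0.068 | 1.138 | 1.50 | 2.25 |
| 18,904 and 17,543 | 10,200 | 0.020 | 1.250 | 2.00 | 2.25 |

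**A non-significant result.** At hazard ratio 1.2 with 839 per group the lower limit is 0.998, so threshold B does not exist. Threshold A does: 1 + 0.20/(0.50 − 0.24) = 1.77. With 1,534 per group the two are 1.16 and 1.77.

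**Other prevalence pairs** (hazard ratio 1.3, 1,534 per group), A versus B: 8.5 versus 2.9 for 30% and 20%; 3.7 versus 1.9 for 50% and 30%; 2.8 versus 1.7 for 30% and 10%. The size of the gap changes, its direction does not.

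**Scale.** Suppose the hazard ratio of 1.3 were entered directly, giving 2.25. The comparison depends on how confounder strength is expressed. For risk-ratio strength, the hazard ratio is first converted by RR = [1 − (1 − risk)^HR]/risk. At 25% risk that is 1.248, and R = 1 + 0.248/(0.50 − 0.2496) = 1.99.

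| One-year risk | R if strength is a hazard ratio (large-sample Cox value) | R if strength is a risk ratio (after conversion) |
|---|---|---|
| 1% | 2.25 | 2.24 |
| 10% | 2.26 | 2.15 |
| 25% | 2.29 | 1.99 |
| 40% | 2.34 | 1.83 |
| 50% | 2.38 | 1.72 |

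Direct entry therefore slightly understates the required strength in the first case and overstates it in the second. The difference is negligible for rare outcomes.

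**The case against.** The best defence is that the paragraph after the disputed clause already aims at effect sizes and uses an array over confounder strength and imbalance, from which the point where the estimate reaches 1 can be read. A confidence-limit tipping point is also a legitimate quantity, and the plan sets no rule that labels findings robust or fragile. In the largest subgroup the gap is modest in the illustration (2.00 against 2.25). All of this stands. It limits the harm, but it leaves in place a written definition that contradicts the stated aim.

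A reader might infer more than the documents support:

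- That the plan applies a risk-ratio formula to Cox hazard ratios. It does not say so. The source of the observed relative risk is undefined, which is a gap and not a demonstrated misuse.
- That entering a hazard ratio would always overstate the confounding needed. The direction depends on the confounder's scale, and the size depends on how common the outcome is.
- That the primary outcome is left out. The plan says "The primary effectiveness outcome will be time to psychiatric hospitalization", and the array covers the study outcomes in general; BMI and diabetes is only an illustration.
- That this is the only safeguard against confounding by indication. Diagnostic subgroups and propensity weighting are also planned; the point concerns unmeasured confounding alone.

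**Conclusion.** The point holds as a fault of definition and labelling. The plan equates two thresholds that differ for every significant result, and the one that it writes down does not measure full explanation. In the illustration the significance threshold runs from about 1.03 to 2.00 as groups grow from 428 to about 18,000 patients, while the null threshold stays at 2.25. These figures rest on the assumed hazard ratio, event risk, prevalences and constant hazards. That the significance threshold is lower, depends on sample size, and is absent for non-significant results does not rest on them.

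The scale is a secondary gap in specification. It matters mainly when a hazard ratio for a common outcome is combined with risk-ratio confounder inputs: 2.25 against 1.99 at an assumed 25% risk. The documents give no hospitalization rate, so how far this applies to the primary outcome is unknown. The array analysis as a whole is not invalidated.

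**What to change.** In the paragraph on quantitative sensitivity analyses:

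1. Delete loss of significance as the definition of full explanation.
2. For each main result, report two separately labelled tipping points: the confounding that brings the point estimate to 1, and the confounding that brings the confidence limit nearest 1 to 1. Give the second only when the result is significant.
3. State the scale of the observed relative risk and express confounder strength on that same scale. If confounder inputs are risk ratios and the outcome is common, as psychiatric hospitalization may be, convert the hazard ratio first and state the risk used.

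The cost is a wording change and slightly more reporting. Some findings will look less robust on the confidence-limit version than on the estimate version, and the report should explain why. No new estimand is needed.
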